### **Specific Aims**

1. Determine if HFOT tracheostomy is superior to conventional oxygen therapy at preventing postoperative complications
  - a. Determine the association between HFOT tracheostomy collar and postoperative pulmonary complications
  - b. Determine the association between HFOT tracheostomy collar and time to tracheostomy decannulation
  - c. Determine the association between HFOT tracheostomy collar and total length of stay after surgery

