#### Hospital Care

- Care of patients will follow the University of Florida Jacksonville's standardized head and neck protocol (**Figure 1**)
- Analgesia management will be standardized:
  - Scheduled
    - Ibuprofen 600 mg q6 hours scheduled for 72 hours
    - Acetaminophen 650 mg q6 hours scheduled
    - Methocarbamol (Robaxin): 500 mg q 8 hours scheduled
    - Gabapentin 300 mg TID--can scale up if needed to 600 TID after 2 days
  - PRN
    - Oxycodone 5-10 mg q4-6 hours PRN
  - Breakthrough/PRN:
    - Morphine 1-4 mg IV q 2-4 hours PRN
    - Hydromorphone 0.5-1 mg IV q 2-4 hours PRN

NCT05362526

IRB202102700

9/22/22

- Fluids will be standardized to prevent fluid overload/pulmonary edema, and ordered based on body weight, and ideal body weight for obese patients. Fluids will be discontinued once the patient is taking adequate intake by mouth or via tube feeds
- Weaning of the tracheostomy will be standardized
  - If patient is deemed clinically acceptable by team (no sign of pulmonary complication as defined above), the tracheostomy will be downsized on postoperative day 4, to a 6-0 fenestrated uncuffed Shiley, and will undergo occlusive capping as soon as tolerated after the downsize
  - Once the patient tolerates 24-hour capping, and deemed clinically acceptable for decannulation, the tracheostomy will be removed
  - Tracheostomy may be determined necessary if capping not tolerated, or needed for aggressive pulmonary toileting
- Consultation for specialty management of subject comorbidities will be permitted

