#### Clinic Follow Up Appointments

- Subjects will follow up in clinic between 1-2 weeks postoperatively from their discharge date
- Vitals and physical exam will be performed, and all subjects will be monitored for adverse events
- Subjects will be closely followed every 1-3 weeks for the first 2 months after surgery
- At 12 days postoperatively all subjects will be called or evaluated in clinic for the final screening for adverse events or pulmonary complications

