## **Outcome Measures**

- Primary
  - **Incidence of post-operative pulmonary complication within 14 days after surgery**
    - Postoperative pulmonary complication will be defined as
      - Atelectasis or infiltrate diagnosed by radiologist on any postoperative chest radiograph within first 14 days or discharge (whichever occurs first)
      - Pneumonia
        - *Diagnosis is suggested by a history of cough, dyspnea, pleuritic pain, or acute functional or cognitive decline, with abnormal vital signs (e.g., fever, tachycardia) and lung examination findings. Diagnosis should be confirmed by chest radiography or ultrasonography.* [15]
    - Chronic pulmonary obstructive disease exacerbation
      - *An event in the natural course of the disease characterized by a change in the patient's baseline dyspnea, cough, and/or sputum and beyond normal day-to-day variations, that is acute in onset and may warrant a change in regular medication in a patient with underlying COPD* [16]
    - Adult respiratory distress syndrome (Berlin definition)
    - Need for reintubation/mechanical ventilation
    - Need for non-invasive mechanical ventilation
  - Secondary
    - **Time to tracheostomy decannulation** (half days)

NCT05362526

IRB202102700

9/22/22

- **Hospital length of stay after surgery** (half days)
- **Need for antibiotics for pulmonary complication** (escalation to broad spectrum, addition of a second antibiotic, antibiotics past post-operative day 7)
- **Need for pulmonary physiotherapy** (acapella, flutter, etc.)
- **Discharge destination:** Home vs nursing facility vs rehabilitation

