## **Statistical Analysis**

### Sample Size Rationale

A sample size of 164 patients, 82 in each arm, is sufficient to detect a clinically important difference of 20% in the proportion of postoperative pulmonary complications between arms using a two-tailed z-test of proportions with 90% power and a 5% level of significance. This 20% difference represents 10% of postoperative pulmonary complications using HFOT and 30% of postoperative pulmonary complications in the control arm. Assuming a 10% rate of withdrawal, we will need to recruit 91 patients per arm to be adequately powered to detect the difference.

An interim analysis of the proportion of postoperative pulmonary complications is planned after 100 subjects (50:50) are enrolled to assess whether there will be overwhelming evidence of a benefit from HFOT, as compared with conventional oxygen therapy, or of harm in any study group. As a consequence, the p-value for the primary comparison between the two arms will be adjusted to conserve an overall significance level of 0.05[17]. Descriptive summaries will be frequencies and percentages for categorical variables and means, standard deviations, medians, and quartiles for continuous variables. The primary analysis will compare the difference in the proportion of postoperative pulmonary complications

between the intervention group and the control group. This difference is assessed using univariate analyses and ANCOVA (Analysis of Covariance) models. Demographic and baseline characteristics between groups are assessed using the non-parametric Wilcoxon Rank-Sum test for continuous data, and Pearson Chi-squared test or Fisher's Exact test (when expected frequencies are small) for categorical data. The secondary outcomes will be analyses using the same statistical methods, based upon the data distributions. Data analyses will be performed by a statistician with the Center for Data Solutions.

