**Figure 1. Oral and Maxillofacial Surgery Free Flap Management Protocol by Postoperative Day**

	Day 0	Day 1	Day 2	Day 3	Day 4	Day 5	Day 6	Day 7	Discharge Goals
Trachea/Airway		Trach suction by respiratory every 6 hours  Albuterol/ipratropium nebulized q 6 hours scheduled until decannulated or discharged			Trach changed to 6 cuffless, fenestrated tube CAN CAP IF READY	Decannulate when capped >24 hours			Trach tube out or all at-home supplies and care instruction provided
Flap Donor Site	Dressing kept until discharge								Dressing to be changed at first follow-up
Skin Graft Donor Site	Dressing kept until discharge								Skin graft dressing change at first follow-up
Flap Checks	Every two hours			Every 4 hours after 48 hours					Flap checks discontinued upon discharge
Drains	JP drains to bulb suction with output, recorded		Discontinue drains when <30 ml / 24 hours						
Laboratory		Complete blood count, basic metabolic panel, magnesium, phosphorus, others as indicated each morning		Discontinue labs when IVF discontinued					
IV Fluids, Antibiotics	One dose of abx prior to incision	Continue antibiotics 3 doses post-op	Titrate IV fluids to heplock to accommodate TF rate	D/C IVF when TF at goal		Antibiotics until POD 7			

NCT05362526  
IRB202102700  
9/22/22

Pain Management	IV pain meds	Oral pain medication with IV for BTP		Narcotic pain meds weaned as tolerated					Pain control on oral medication alone
Delirium Tremens Prophylaxis	CIWA protocol as appropriate								
Activity	Bedrest	Bedrest	Bedrest or sitting on edge of bed	To chair	Ambulate	Ambulate	Ambulate	Ambulate	Baseline mobility or independent at home
Nutrition	NPO. Meds only pre NGT	After 24 hours, start tube feeds				P.O. trials or start bolus tube feed	D/C NGT or arrange for TF upon D/C		Tolerate at least full liquids or home with enteral feed teaching machine
Catheter	Maintain Foley catheter			D/C Foley					
Gastrointestinal	PPI to start post-operatively Stool softeners							Discharge with normal bowel function, no GI bleed	
Thromboprophylaxis	Compression stockings, SCDs during and after surgery	Prophylactic lovenox, ASA 325mg/d to start at 24 hours							Discharge with no deep vein thrombosis, or pulmonary embolism
Miscellaneous		Consult PT, nutrition, respiratory, case manager, speech therapy							Smooth and timely discharge with high patient satisfaction

IRB:202102700

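### Time to decannulation (Aim 1b) has no end of observation and no rule for patients discharged with the tube in, and the methods assigned to it do not handle incomplete times

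*Combined protocol and SAP*

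**What the plan says.** **The endpoint.** Aim 1b is: "Determine the association between HFOT tracheostomy collar and time to tracheostomy decannulation". Aim 1c is: "Determine the association between HFOT tracheostomy collar and total length of stay after surgery". Outcome Measures lists "Time to tracheostomy decannulation" first among the secondary outcomes, in half days, with no further definition.

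**The analysis.** The Statistical Analysis section, in the text under Sample Size Rationale, says: "The secondary outcomes will be analyses using the same statistical methods, based upon the data distributions". The methods named there are univariate analyses and ANCOVA for the primary comparison, and Wilcoxon rank-sum, Pearson chi-squared and Fisher tests for baseline data. Continuous variables are summarised by means, standard deviations, medians and quartiles. No censoring rule, Kaplan-Meier estimate, log-rank test or Cox model appears.

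**Patients without a completed time.** Removal is conditional. Hospital Care says: "Once the patient tolerates 24-hour capping, and deemed clinically acceptable for decannulation, the tracheostomy will be removed". It also foresees keeping the tube when capping is not tolerated or for pulmonary toileting. The airway discharge goal in Figure 1 is "Trach tube out or all at-home supplies and care instruction provided", so discharge with the tube in is foreseen.

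**Observation.** The radiographic part of the primary outcome is limited to films "within first 14 days or discharge (whichever occurs first"). No limit of any kind is attached to decannulation. Clinic Follow Up Appointments says: "Subjects will be closely followed every 1-3 weeks for the first 2 months after surgery". The content listed for follow-up is vital signs, examination, adverse events and pulmonary complications. Data Collection names the medical record as a source but not how long it is read.

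**The concern.** Patients still cannulated at discharge are the slower ones, so their times are not missing at random. The documents leave three readings open:

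- follow every patient to decannulation;
- analyse only patients decannulated by discharge;
- enter the discharge time as if it were the decannulation time.

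The last two make Aim 1b depend on when patients go home. With equal discharge timing in the two arms, a true benefit is attenuated. If HFOT shortens stay, the shorter stay alone can look like earlier decannulation. If HFOT lengthens stay, a real benefit can be hidden. The trial is unblinded, so a rule chosen after the data are seen would be hard to defend.

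**Working it through.** **The plan's own figure.** There is none for decannulation. The primary sample size reproduces with the pooled formula: n = [1.96·√(2·0.2·0.8) + 1.2816·√(0.3·0.7 + 0.1·0.9)]² / 0.2² = (1.109 + 0.702)² / 0.04 ≈ 82 per arm. It is not touched by this point.

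**Inputs.** From the documents: 82 per arm, downsizing on day 4, and removal after 24 hours of capping, so day 5 is the earliest removal time used. The documents give no decannulation or discharge distribution, so the rest is assumed:
- 20% laryngectomies: 82 × 0.8 ≈ 66 per arm.
- Decannulation on day 5 plus an exponential time, rate 0.35/day for COT and 0.56/day for HFOT. The hazard ratio is 0.56/0.35 = 1.6. The true mean difference is 1/0.35 − 1/0.56 ≈ 1.07 days.
- Discharge on day 6 plus a gamma time (shape 2, scale s), mean 6 + 2s, independent of decannulation.
- Times rounded up to half days.

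**Share discharged with the tube in.** Before rounding this is e^(−λ)/(1 + λs)². Rounding discharge up adds about 0.25 day, a factor of e^(−0.25λ). For s = 3 and λ = 0.35: 0.705 × 0.238 × 0.916 ≈ 15%. The same formula gives 7% for λ = 0.56.

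**Power with equal discharge timing, hazard ratio 1.6** (1,500 simulated trials per scenario; standard error at most √(0.25/1500) ≈ 1.3 points):

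| Tube in at discharge, COT v HFOT | 7% v 3% (s = 6) | 15% v 7% (s = 3) | 32% v 18% (s = 1.2) |
|---|---|---|---|
| Rank-sum, completers only | 51% | 38% | 18% |
| Rank-sum, discharge time entered | 63% | 59% | 52% |
| Rank-sum, worst rank at discharge | 62% | 61% | 56% |
| Log-rank censored at discharge | 72% | 70% | 64% |

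With dates followed to a common day 60, rank-sum power is 64% and log-rank power 76%, each with 5% false positives. Among completers, the true difference of about 1.06 days after rounding appears as 0.80, 0.56 and 0.26 days.

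The fair comparison for completers-only is rank-sum with full follow-up. In the first column that loss is 64 − 51 = 13 points. The further 72 − 64 = 8 points up to log-rank come from the choice of test under simulated proportional hazards.

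**False positives with no decannulation effect and a shorter HFOT stay** (nominal 5%; 10,000 trials per scenario, with 1,500-trial reruns giving the ranges):

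| Mean stay, COT v HFOT | Completers only | Discharge time entered | Worst rank at discharge | Log-rank censored at discharge |
|---|---|---|---|---|
| 11 v 10 days | 6-7% | 6% | 5% | 6% |
| 11 v 9 days | 13% | 9% | 7% | 6% |
| 11 v 8.4 days | 23-24% | 14% | 9% | 5% |
| 12 v 8.4 days | 30-31% | 18% | 11% | 5% |

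From 11 v 9 days on, nearly all completers-only rejections favour HFOT. Worst rank at discharge errs in the other direction, because more HFOT patients leave with the tube in. With equal timing (s = 2.5) completers-only rejects in 4.5%. With 57 to 74 per arm (30% or 10% laryngectomies), completers-only rejects in 12-15% at 11 v 9 days and 28-35% at 12 v 8.4 days.

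**Longer HFOT stay** (9 v 11 days), hazard ratio 1.6: completers-only power is 10%, against 68% for log-rank.

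**Discharge related to decannulation** (correlation 0.5), no effect: log-rank censored at discharge rejects in 5.8% and 6.5% at 11 v 9 and 12 v 8.4 days. Censoring at discharge is therefore not a full cure, and a common window is needed as well.

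**The case against.** Four objections carry weight.

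1. A reader might infer that every method in the plan needs a completed time for each patient. That goes too far. ANCOVA and means do, but a rank-sum test needs only an ordering. With a worst rank for tubes still in at the end of a common window it is valid. The phrase about data distributions leaves some latitude too. What stands is that no ranking rule or window is stated, and that wording about distributions does not supply one.
2. A reader might infer that observation stops at discharge and that the result will be biased. The documents do not say so. The discharge limit is written only for the radiographic part of the primary outcome, and visits run to 2 months. Following patients to decannulation is feasible and fits the wording. It is not committed to, however, and the date is not among the items listed for follow-up.
3. The power gap between completers-only and log-rank is not all due to lost times; part is the efficiency of log-rank under the simulated model. Most of the power loss under equal timing also belongs to the completers-only reading.
4. The large false-positive rates need large, assumed differences in stay. At 11 v 10 days the rate is close to nominal, and if few patients leave with the tube in, the effect is small.

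**Conclusion.** The omission is certain: a named aim has a time-to-event endpoint, unfinished times are foreseen, and the plan gives no window, no post-discharge collection of the date and no rule for tubes still in. The bias is conditional, arising only if observation stops at discharge. Its size rests on the assumed decannulation and discharge distributions and on the share of laryngectomies, none of which the documents give. Under those assumptions the harm runs from negligible to a rank-sum power of 18% instead of 64%, or a false-positive rate of about 30%. The primary outcome and its sample size are unaffected. This is a cheap improvement that should be made before analysis, not a flaw that invalidates the trial.

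**What to change.** State the following for this endpoint:

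1. **Observation.** Record the decannulation date at discharge and at the clinic visits already planned to 2 months, with one common window for all patients.
2. **Analysis set.** Randomised patients with a tracheostomy. Say that total laryngectomy patients, who receive a laryngectomy tube, are outside this endpoint.
3. **Analysis.** A log-rank test and Cox model stratified by randomisation subgroup, censoring tubes still in at last contact or at the end of the window. A worst-rank rank-sum test over the same common window is an acceptable, somewhat less efficient alternative. ANCOVA or rank-sum on completed or discharge-truncated times is not. Any deaths before decannulation can be handled as a competing event.

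The cost is SAP wording and one date field. No visit is added and no clinical management changes.

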### **Possible Discomfort and Risks**

- Participants may be in some discomfort due to their planned head and neck surgery. Patients in this study will be receiving our current standard of care (COT) or HFOT therapy, which is also an established standard of care modality. Thus, risks to patients are low, and have not been observed in similar studies.

There is the minimal risk of a participant's privacy being compromised. Several measures to ensure the privacy protection of those enrolled in the study will be in place as described in the Patient Privacy and Protection section on page 11.

### **Possible Benefits**

- There may be a benefit to those randomized to HFOT oxygen versus COT or there may not be any difference between the two in reducing postoperative pulmonary complications. The results of this study will help guide best practices in the postoperative care of head and neck cancer surgical patients.

### **Conflict of Interest**

NCT05362526  
IRB202102700  
9/22/22

- This study is funded by Fisher and Paykel, Inc., manufacturers of the Airvo 2 high flow device
- However, the sponsor company cannot interfere with the study, data collection, or statistical analysis

### **Data Safety Monitoring Board**

- No experimental interventions are taking place, as HFOT tracheostomy delivery and conventional oxygen therapy are both well established and widely used modalities.
- The PI will monitor for any adverse events. If any adverse events are identified, they will be reported to the IRB in the required time frames.

**Anticipated study duration:** 14-24 months

**Figure 1. Oral and Maxillofacial Surgery Free Flap Management Protocol by Postoperative Day**

	Day 0	Day 1	Day 2	Day 3	Day 4	Day 5	Day 6	Day 7	Discharge Goals
Trachea/Airway		Trach suction by respiratory every 6 hours  Albuterol/ipratropium nebulized q 6 hours scheduled until decannulated or discharged			Trach changed to 6 cuffless, fenestrated tube CAN CAP IF READY	Decannulate when capped >24 hours			Trach tube out or all at-home supplies and care instruction provided
Flap Donor Site	Dressing kept until discharge								Dressing to be changed at first follow-up
Skin Graft Donor Site	Dressing kept until discharge								Skin graft dressing change at first follow-up
Flap Checks	Every two hours			Every 4 hours after 48 hours					Flap checks discontinued upon discharge
Drains	JP drains to bulb suction with output, recorded		Discontinue drains when <30 ml / 24 hours						
Laboratory		Complete blood count, basic metabolic panel, magnesium, phosphorus, others as indicated each morning		Discontinue labs when IVF discontinued					
IV Fluids, Antibiotics	One dose of abx prior to incision	Continue antibiotics 3 doses post-op	Titrate IV fluids to heplock to accommodate TF rate	D/C IVF when TF at goal		Antibiotics until POD 7			

NCT05362526  
IRB202102700  
9/22/22

Pain Management	IV pain meds	Oral pain medication with IV for BTP		Narcotic pain meds weaned as tolerated					Pain control on oral medication alone
Delirium Tremens Prophylaxis	CIWA protocol as appropriate								
Activity	Bedrest	Bedrest	Bedrest or sitting on edge of bed	To chair	Ambulate	Ambulate	Ambulate	Ambulate	Baseline mobility or independent at home
Nutrition	NPO. Meds only pre NGT	After 24 hours, start tube feeds				P.O. trials or start bolus tube feed	D/C NGT or arrange for TF upon D/C		Tolerate at least full liquids or home with enteral feed teaching machine
Catheter	Maintain Foley catheter			D/C Foley					
Gastrointestinal	PPI to start post-operatively Stool softeners							Discharge with normal bowel function, no GI bleed	
Thromboprophylaxis	Compression stockings, SCDs during and after surgery	Prophylactic lovenox, ASA 325mg/d to start at 24 hours							Discharge with no deep vein thrombosis, or pulmonary embolism
Miscellaneous		Consult PT, nutrition, respiratory, case manager, speech therapy							Smooth and timely discharge with high patient satisfaction

IRB:202102700
